Title of the Study: CCRC: Randomized trial of L-arginine in severe asthma patients grouped by exhaled nitric oxide levels (NCT #01841281)

Principal Investigator: [name], MAS

Updated: December 15, 2019

Last IRB Approval Date: July 16, 2018

PROTOCOL

PURPOSE AND PROCEDURES:

1. Describe the study format (pilot, phase I, phase II, or III) and whether it is single or multi-center; industry-sponsored or investigator initiated; and the funding source.

This is an investigator-initiated, early phase II study funded by NHLBI.

2. Describe the specific aims of the study, research methods and procedures.

We hypothesize that a subset of adult severe asthma patients will respond to supplemental L-arginine and derive clinical benefit from the addition of this therapy to standard-of-care medications. We hypothesize that these patients will have lower exhaled NO concentrations (<20 ppb) than -non-responders. The aim is:

1. To test the hypothesis that adult severe asthma subjects with exhaled breath NO concentrations <20 ppb will have fewer American Thoracic Society (ATS)-defined asthma exacerbations over 3 months when treated with L-arginine compared to subjects with FeNO > 25.

The major impact of this study will be to identify the adult severe asthma cohort that will benefit from supplemental L-arginine therapy to define the underlying mechanisms of arginine benefit in asthma. This follows our initial 20 subject trial of L-arginine in asthma subjects ([name] et al., Pharmaceuticals 2011) that was designed to determine how L-arginine was metabolized (by testing serum markers) and whether certain participants had clinical benefit.

To do this, we will recruit a total of 50 ATS-defined asthmatic subjects with ≥ 2 asthma exacerbations in past two months and enroll them in a randomized, blinded, placebo-controlled, cross-over designed trial of L-arginine and placebo. We will compare 25 subjects with -low FeNO <20 with 25 subjects that have -high FeNO > 25 ppb.

Study Design:

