Research subjects are encouraged to report any adverse effects to the PI, Co-PI or study personnel, who will suggest ways to minimize the problems. The PI and Co-PI will review all adverse events. The review may lead to the recommendation that the subject be withdrawn from the study. When appropriate, the subject will be referred to their primary physician. In accordance with NIH regulations, reportable adverse effects arising from any of the procedures will be submitted promptly to the UC Davis Office of Human Research Protection and the PI will be notified of any subsequent reporting by the UCD OHRP to the NIH. Although they are not anticipated to occur, Unanticipated (non-serious) or Serious Adverse Events will be reported to the IRB within 5 working days of awareness of the event. Copies of reports should be received by the IRB office no later than 15 calendar days after the event. In addition, adverse events in all categories will be included in the PIs annual reports to the IRB as required by the federal regulations. All subjects will be seen by the PI and co-investigators. Research

subjects are followed by their regular physicians, so they will continue to receive usual care. [name] and co-investigators will review safety parameters prior to enrollment. The PI reviews and reports on the progress of the study on a semi-annual basis. The PI will monitor study progress, outcomes and participant safety, and may make recommendations on changes to the study protocol. The PI will review safety on an ongoing basis. All reportable adverse events will be compiled, and reported in summary form, on an annual basis to the IRB, and at the conclusion of the study. Unanticipated adverse events and serious adverse events will be reported to the IRB. The protocol is reviewed annually by the IRB in conjunction with adverse event information.

ClinicalTrials.gov Requirements: Aims 1 will be reported on the clinicaltrials.gov website. We will register with ClinicalTrials.gov within 21 days after enrollment of the first patient. Summary result information will be reported within one year of completion of the trial.

5. If the study involves the use of placebo, justify why this is appropriate.

While this study includes a placebo, it is an -add-on placebo. Subjects will be on their standard asthma medication. This is part of the inclusion criteria for the study. This will be monitored at study visits.

BENEFITS:

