1. Address if there is a benefit to individual subjects or to the group or class.

There is no benefit to the participant in this study. If we find that L-arginine improves asthma exacerbation rates in severe asthma patients, this will be a significant advance. Also, if we find that the exhaled breath condensate (EBC) method confirms established NO profiles for asthmatics, we can again use the EBC method for further research and this non-invasive method would be an advance. Overall, we must state that there is no known direct benefit to the current study population.

2. Address if there is no direct benefit to the subject.

There is no benefit to the subjects/participants in the study.

RISK-BENEFIT RATIO:

1. Address whether the risks to subjects are reasonable in relation to the benefits.

This study is a minimal risk for Aim I. No serious adverse events are anticipated. The only interventions will be a physical exam, questionnaire, routine spirometry (in healthy controls), blood draw, and exhaled gas collection. There is unlikely to be much direct benefit to individual participants in the short term, although it is apparent that some patients recruited from the community need modification of their treatment which can be advised to their general practitioner. It is hoped that the results from the study will lead to the development of better treatments for severe asthma in the future, and so in the long term, all participants with severe asthma may benefit.

COSTS/COMPENSATION TO SUBJECTS:

1. If the study involves the possibility of added expenses to the subject or to a third party, such as an insurer (e.g., longer hospitalization, extra laboratory tests, travel) address the magnitude of those expenses and how this is justified.

The study will not include planned added expenses to the participant.

2. Describe the amount and type of compensation that will be paid to subjects and how that compensation will be staged/pro-rated.

Aim #1 Clinical Trial: Subjects will be compensated \$40/study visit or \$160/total at time of completion of L-arginine trial. Reimbursement is for time and travel.

DISCLOSURE OF PERSONAL AND FINANCIAL INTEREST:

1. Disclose any personal and financial interest in the research as well as the extent of personal and financial interest in the sponsor.

The investigators have no financial interest in the research. It is funded by NIH.

INVESTIGATIONAL DRUG (if applicable):

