Oral supplementation with 6-21 g per day has been studied and is safe (42), and an important clinical trial in pulmonary hypertension adopted the same dosage (0.1 g/kg), without any untoward effects (40). High level doses of L-arginine may lead to excessively high levels of asymmetric dimethyl arginine (ADMA), a NOS inhibitor, therefore, in our pilot study and in the proposed study we choose an L-arginine dose in the low -therapeutic range.

2. Describe previous studies on humans.

We have published our finding of L-arginine pilot study at this dose in asthmatics in 2011 ([name] et al. Pharmaceuticals 2011; full reference immediately below). It is safe with minimal side effects. Furthermore, there

is a 15-year history of human studies with L-arginine.

3. Address whether this study will have a Data Safety Monitoring Board in place.

Data and Safety Monitoring Plan (DSMB)

As this study will be considered moderate risk because of the research bronchoscopy associated with a Phase II clinical trial, a biannual review of all study visits clinical data, bronchoscopy reports, and any adverse events will be performed by an independent Data Safety Monitoring Board. As required by NIH supported clinical centers, the UC Davis CTSC has the mechanism to establish and maintains DSMBs for diverse clinical trials throughout the institution. We will install a DSMB with expertise in clinical trials, regulatory support, interventional bronchoscopy and statistics. This board will be submitted to the UC Davis IRB for approval. Names of individuals who will serve on the data safety monitoring board:

Statistical Analysis Methods

Study design and participants

We used a randomized, triple-blinded, placebo-controlled, cross-over design trial to evaluate the efficacy of oral L-arginine as an add-on therapy in adults with severe asthma. We performed a two-group study stratifying participants by fractional exhaled nitric oxide (FeNO) levels, "low" FeNO <20 ppb versus "high" FeNO > 25 ppb. The patients were recruited from the University of California-Davis Asthma Network (UCAN™) clinic.

Outcomes

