The primary endpoint was the total number of "moderate" exacerbations during the 12-week interventional period, as defined by recent the ATS/ERS 2009 statement [2]. A moderate asthma exacerbation is defined as any of the following: 1) a drop in am PEF>30% from baseline on two consecutive days, 2) need for initiation of oral steroids or an increased dose of inhaled corticoid steroid on any two consecutive days, 3) doubling of short-acting β -agonist use (e.g. number of puffs of albuterol)/ day for 2 consecutive days [3-5]. The secondary clinical endpoints were recorded at each of the six study visits, these included: 1) asthma control test score, 2) FEV1 (liters), 3) FVC (liters), 4) FEV1/FVC (%), and 5) Weight. The secondary biological endpoints including FeNO and untargeted metabolites.

Metabolites measurement

Longitudinal plasma metabolite levels were measured by hydrophilic interaction liquid chromatography (HILIC) in both positive and negative modes and gas chromatography (GC) mode. The peak intensity was measured for the compounds and were annotated to specific known metabolites. Relative standard deviation (RSD) for each compound found in more than one mode in quality control samples were calculated and the intensities of compound with lowest RSD was chosen for the downstream analysis.

Clinical trial analysis

For the sample size calculation, we used a conservative power estimate based on t-test analysis of 2x2 cross-over design [6]. For a sample size of 50 people, we would have 95% power to detect a 0.6 standard deviation change in the mean lung function at $\alpha = 0.025$ and accounting for 10% attrition rate. Improvements of this magnitude are consistent with those reported in recent crossover trials in asthma with either FEV1 [7], symptoms scores [8], or AM PEF [9] as outcomes. Statistical analyses for the clinical trials were performed using SAS University Edition (SAS Institute Inc., Cary, NC, USA.) and R (public access). Data were analyzed on an intention-to-treat basis and the significant level was defined by p value less than 0.05. A generalized linear mixed model was used for analysis accounting for correlated repeated measurements which enable us to account for expected missing data points [10]. This model considered differences in baseline levels of function, by allowing for person-specific random effects (random intercepts). The distribution of exacerbation events was assumed to be a Poisson distribution. For

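### Aim 1 is worded as a comparison of FeNO groups on L-arginine, the SAP's primary test is drug versus placebo, and the one power figure covers neither exacerbation comparison

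*Combined protocol and SAP*

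**What the plan says.** Purpose and Procedures, item 2, states one aim: adults with severe asthma and FeNO below 20 ppb "will have fewer American Thoracic Society (ATS)-defined asthma exacerbations over 3 months when treated with L-arginine compared to subjects with FeNO > 25". The hypothesis just before it concerns response. A subset of patients is expected to respond to L-arginine, and "We hypothesize that these patients will have lower exhaled NO concentrations (<20 ppb) than -non-responders". The same item gives the study's main impact as finding the cohort that benefits. The design is a placebo-controlled cross-over with 25 subjects planned in each FeNO group.

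Statistical Analysis Methods opens with a broader purpose: "to evaluate the efficacy of oral L-arginine as an add-on therapy in adults with severe asthma". Under Clinical trial analysis, the primary hypothesis is carried by an indicator for active treatment. Carryover and period effects are looked at first, then the treatment effect is tested, and the treatment-by-FeNO term is examined. Significance is p below 0.05, with no test named.

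On sample size, "we used a conservative power estimate based on t-test analysis of 2x2 cross-over design"; with 50 people, "we would have 95% power to detect a 0.6 standard deviation change in the mean lung function", at alpha 0.025 and allowing for 10% attrition. For the primary endpoint, "The distribution of exacerbation events was assumed to be a Poisson distribution", with person-specific random intercepts.

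Two other places bear on reporting. Risks, item 4, says that "Aims 1 will be reported on the clinicaltrials.gov website". Benefits, item 1, says: "If we find that L-arginine improves asthma exacerbation rates in severe asthma patients, this will be a significant advance".

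**The concern.** Three different questions sit under one aim.

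- **The literal wording** compares FeNO groups while on drug. FeNO is not randomised, so a lower count in the low-FeNO group could be prognosis alone.
- **The SAP's primary test** is drug versus placebo overall. A positive result would say nothing about FeNO.
- **The stated interest**, who benefits, is the difference between FeNO groups in the within-person drug effect. That term is in the model but has no explicit standing.

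The 95% power figure is easily read as covering the primary test or the aim. It is for mean lung function, whereas both the primary endpoint and Aim 1 count exacerbations.

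A separate point concerns the error bars. A random intercept absorbs variation between people that is common to both periods. It does not absorb extra variation from one period to the next within a person. If such variation exists, Poisson standard errors are too small for the treatment term and the interaction alike.

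**Working it through.** **1. Reproducing the stated power.** Inputs from Clinical trial analysis: 50 people, 10% attrition, 0.6 SD, alpha 0.025, 2x2 cross-over t-test. Completers: 50 x 0.9 = 45, with 45 - 2 = 43 df. Take 0.6 in units of the SD of the within-person difference. The noncentrality is 0.6 x sqrt(45) = 4.02. Power is 95.2% at two-sided 0.025, and 97.6% at one-sided 0.025 or two-sided 0.05. The first matches the plan. The sidedness is still not settled by arithmetic: if 0.6 is in outcome-SD units and the within-person correlation is assumed to be 0.4, one-sided 0.025 gives 94.9%.

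**2. Same scale, benefit of 0.6 SD in low FeNO only.** Assume 22 low and 23 high completers and equal SDs.

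| Test | Effect (SD) | Standard error (SD) | Noncentrality | Power, two-sided 0.05 | Power, two-sided 0.025 |
|---|---|---|---|---|---|
| Drug vs placebo | 0.6 x 22/45 = 0.293 | 1/sqrt(45) = 0.149 | 1.97 | 49% | 37% |
| Treatment x FeNO | 0.6 | sqrt(1/22 + 1/23) = 0.298 | 2.01 | 50% | 39% |

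The expected 95% CI half-width is 2.017 x 0.149 = 0.30 SD for drug versus placebo and 2.017 x 0.298 = 0.60 SD for the interaction. An interaction of about 0.85 SD is needed for 80% power at 0.05. For 95% power at 0.6 SD, 74 completers per FeNO group are needed (86 at 0.025). All of this is on the lung-function scale of the plan's own figure. None of it is power for exacerbations.

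**3. Exacerbation counts, by simulation.** The documents give no event rates, so every input here is an assumption: 1-3 exacerbations per 12 weeks in high FeNO, and a person effect that is absent or gamma with shape 4 or 2. The period effect is likewise absent or gamma with shape 4 or 2. Rates below are one-sided, nominal 2.5%, with an inert drug and low-FeNO subjects having 20-30% fewer exacerbations on any treatment.

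| Analysis | No period-level variation | With period-level variation |
|---|---|---|
| Poisson, interaction | 2.3-2.6% | about 4-12% |
| Poisson, drug vs placebo | about nominal | about 4-12% |
| Interaction, empirical variance | 2.5-3.5% | 2.5-3.5% |
| On-drug low vs high (Aim 1 read literally) | 8-45% | 8-30% |

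The empirical variance of the log rate ratio in a stratum of n people is n/(n-1) times the sum of (a_i/A - p_i/B)^2. Here a_i and p_i are a person's counts on L-arginine and placebo, and A and B are the stratum totals. The interaction variance is the sum over the two strata, referred to t with 43 df.

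**4. Precision of the interaction on exacerbations.** Assume benefit in low FeNO only, no prognostic difference, the empirical variance and rates 1-3. Power is about 10-28% for a rate ratio of 0.7 and 22-71% for 0.5. The 95% CI for the ratio of rate ratios extends by a factor of about 1.6-3.2 each way.

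**The case against.** **The wording is loose, but the plan resolves it.** The text around Aim 1 speaks of response and benefit, the design is a placebo-controlled cross-over, and the SAP fits the interaction. A reader might infer that the trial will analyse on-drug counts in low versus high FeNO and so has a false-positive rate of 8-45%. The documents do not support that, because no analysis section plans the contrast. The figure shows what the aim's wording would license, under assumed rates, and not what the SAP does.

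**The interaction has a place.** A reader might also infer that it is missing, or has no significance level at all. Neither is right. It appears in the primary-hypothesis paragraph, after the treatment effect and with a weaker verb, which implies a lower rank. The general 0.05 threshold applies to it by default. The sizing alpha of 0.025 might even be 0.05 split over two tests, though the documents do not say so. What stands is that the rank is implied and not stated, and no alpha is dedicated to it.

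**The sample size is not miscalculated.** The 95% reproduces. The gap lies in what it covers: it applies to neither exacerbation test, whichever FeNO group benefits.

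**The Benefits statement is a conditional remark, not an Aim 1 claim,** and the registry sentence promises only that the aim will be reported. Both are correct readings. They show where a misreading could surface, not that one is planned.

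**Period-level overdispersion is a separate matter.** It is, and its size rests wholly on assumed shapes. It belongs here because it affects the interval on the very term the restated aim would report.

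**Conclusion.** The point holds and should be fixed before results are reported. Aim 1 as worded is a non-randomised contrast that the SAP does not analyse. The term that answers the scientific question has no explicit rank, and the only power figure concerns a different endpoint under a common drug effect. That much rests on the text alone.

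The 49% and 50% (37% and 39% at 0.025) rest on borrowing the plan's 0.6 SD for low FeNO only, with equal SDs and even attrition. The 4-12% false-positive range rests on assumed rates and gamma shapes. Without period-level variation the Poisson tests are close to nominal, so this is a vulnerability of the stated model and not a demonstrated error.

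**What to change.** 1. Restate Aim 1 as the ratio of within-person L-arginine/placebo exacerbation rate ratios, low versus high FeNO. Fit it with the FeNO main effect, and report it with each group's rate ratio and CI. Do not use on-drug low-versus-high counts as evidence of benefit.
2. Keep drug versus placebo on exacerbations as primary. Label the interaction secondary, reported as an estimate with 95% CI and no confirmatory claim, so that it needs no alpha.
3. State that the 95% power is for lung function with the same benefit in both FeNO groups, and applies neither to the exacerbation endpoint nor to the FeNO comparison.
4. Use an empirical (robust) within-person variance for the treatment and interaction terms, with the plain Poisson result as a sensitivity analysis.
5. Because the SAP is written in the past tense, report any change to the primary test or its variance and date it relative to unblinding. State the sidedness of 0.025 and whether it is 0.05 split over two tests.

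The cost is wording, one label and a variance option, with no new data or model terms. The price is wider intervals and an imprecise interaction. That low precision is why an estimate is proposed and not a new primary test.

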After signing the informed consent, severe asthma subjects will be enrolled for screening sample collections—exhaled breath samples for exhaled nitric oxide measurements. All subjects will have their medical records and past studies for characterization of their severe asthma as described above. All subjects will breathe into collection devices to collect both exhaled gases.

Study visits 1-4

After reviewing the signed informed consent and answering questions regarding the protocol, severe asthma subjects will be enrolled for sample collections—blood and breath. All subjects will breathe into collection devices to collect both exhaled gas and exhaled breath condensate. The EBC collection device is approved for the measurement of pH and is supplied by a commercial supplier. The subjects will not receive any study medications, biologics, or radioactive materials at this time. The study drug and placebo will be mailed to the subject by the Investigational Drug Service, housed in the UC Davis hospital. This is recharge based service. The visit 1-4 procedures are:

- *Exhaled breath nitric oxide collection:* Exhaled breath samples will be collected by the investigators from each participant at the time of the study visit. Samples will be collected in Mylar bags using the off-line exhaled breath technique, as described in the 2005 ATS/ERS standardized measurement recommendations document. Two breath samples will be collected in individual bags at a flow rate of 250 L/sec, and measurements will be recorded within 12 hours. A pressure gauge at the collection apparatus (standard on the Sievers NO analyzer offline collection apparatus) will allow for the participant and interviewer to control exhaled breath flow rates. All samples from Sacramento participants will be analyzed on a Sievers 280i NO Analyzer (Boulder, CO) in [name] laboratory.
- *Exhaled Breath Condensate (EBC) Collection:* Collections of EBC from each participant will occur immediately after collection of the exhaled breath samples. Participants will breathe into a chilled collection tube for 10 minutes as recommended in the 2005 ATS/ERS statement. Collection tubes will be purchased from Respiratory Research (Charlottesville, VA), a commercial entity that has received FDA approval for measuring EBC pH in subjects with cough. Immediately after collection, the tubes will be frozen on dry ice for transport to [name] lab. Total time of sample collection should be 10 minutes. Breath samples will undergo chemical analysis at [name] laboratory. Volatiles in breath samples will be concentrated using Solid Phase Microextraction (SPME). Analyte compounds will then be loaded on a chromatographic column for a nominal pre-separation and will be detected with a differential mobility spectrometer, according to protocols previously developed in [name] lab.
- *Blood draw* 16 cc of blood will be drawn at each visit. Serum will be collected for cytokine profiling and NOx measurements and L-arginine metabolites. Whole blood will be processed for genotyping.

- *Office Spirometry will be performed with portable office spirometer (Spriolab II).*
- *Physical examination and symptom questionnaire*

Brief Study outline: 1 screening visit and 4 study visits

- Screening Visit
- Explanation of protocol
 - Informed consent
 - History and physical examination
 - Two exhaled NO measurements (to determine if subjects > or < 25 ppb)
- Study Day 1
- History and physical examination (brief) to verify stable clinical status
 - Blood collection #1
 - Spirometry #1
 - Exhaled NO measurement #1
 - Sputum collection #1
-
- Respiratory symptom questionnaire #1
 - Start symptom and peak flow diary
 - Start oral L-arginine or placebo
- Study Day 80
- Updated clinical history
 - Blood collection #2
 - Spirometry #2
 - Exhaled NO measurement #2
 - Sputum collection #2
 - Respiratory symptom questionnaire #2
- Study Day 110
- Updated clinical history
 - Blood collection #3
 - Spirometry #3
 - Exhaled NO measurement #3
 - Sputum collection #3
 - Respiratory symptom questionnaire #3
- Study Day 190
- History and full physical examination
 - Blood collection #4
 - Spirometry #4
 - Exhaled NO measurement #4
 - Sputum collection #4
 - Respiratory symptom questionnaire #4
 - Stop oral L-arginine or placebo

5. If blood samples will be collected, identify in what manner:

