The study locations will be the existing UC Davis Pulmonary clinics that house the UCAN clinics, the UC Davis CTSC Clinical Research Center that is also located in the VA Mather Hospital, the locations are: UC Davis Pulmonary clinics (including the UC Davis Asthma Network clinic) at [name]. One primary source of patients will be the UC Davis Asthma Network clinics (UCAN), where [name] serves as Co-Director. [name] and colleagues see many subjects with diagnosed severe asthma and many of these subjects will fit the criteria for enrollment in this study. We maintain a database of over 700 subjects treated by us in the past 10 years. The UCAN asthma clinic saw approximately 720 referred patients from 1999-2007. 77% of the referrals were women with a mean age of 46.3±15.3 (mean± SD) years. (Kivler et al JACI 2002, 109:S314, Kivler et al. AJRCCM 2003, 167:A209).

4. Specify the age of the research subjects.

Asthmatic patients aged 18-80 will be enrolled.

5. List all criteria for including and excluding subjects.

Inclusion and Exclusion Criteria: Inclusion a) Adult patients >18 years or older with ATS definition of severe asthma, b) History of recent exacerbations ≥ 2 in past 2 months) or Asthma Control Test score < 20/25. Subjects will meet this definition based on the use of high dose ICS and LABA use (Table 3) plus an even distribution among minor criteria 2-5. *Exclusion:* a) Less than 18 years of age; b) baseline FEV1 <30% predicted, c) pregnant or nursing women, e) current smokers or subject with >15 pack year history, f) any history of intolerance of, or reaction to, L-arginine.

Controller Medications for Study: Upon enrollment, all subjects will be treated with high dose ICS and LABAs throughout the 8-month period. The overwhelming majority of the UCAN™ patients are on one of these two ICS. In addition, all subjects will be on scheduled LABAs, and will be aware of the FDA Black Box warning on these medications. Additional controller medication including leukotriene inhibitors will not be stopped, and it is expected that the use of these other medications will be roughly equal between the two groups.

6. If women and minorities are excluded, provide rationale for such exclusion.

Women and minorities will not be excluded. Many enrolled subjects will be women as severe asthma in adults is approximately 60-70% women.

SPECIAL/VULNERABLE POPULATION (if applicable):

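### Screening sorts FeNO at a single 25 ppb cut while the trial's groups are <20 and >25 ppb, and no eligibility criterion keeps subjects at 20-25 ppb from being randomised

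*Combined protocol and SAP*

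**What the plan says.** Three places in the combined protocol and SAP define the FeNO groups, and they agree.

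- Purpose and Procedures, item 2, Aim 1 states its hypothesis as "adult severe asthma subjects with exhaled breath NO concentrations <20 ppb will have fewer American Thoracic Society (ATS)-defined asthma exacerbations over 3 months". The setting is L-arginine treatment, and the comparator is the group above 25 ppb.
- Same item, design paragraph: "We will compare 25 subjects with -low FeNO <20 with 25 subjects that have -high FeNO > 25 ppb".
- Statistical Analysis Methods, Study design and participants: "We performed a two-group study stratifying participants by fractional exhaled nitric oxide (FeNO) levels", followed by the same limits, below 20 ppb for low and above 25 ppb for high.

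Under these definitions the band from 20 to 25 ppb, both ends included, belongs to neither group.

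Two other places bear on who gets in.

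- Brief study outline, Screening Visit: "Two exhaled NO measurements (to determine if subjects > or < 25 ppb". The value 20 ppb does not appear there.
- Subject Selection, item 5, which is meant to list all criteria, opens its inclusion list with "Adult patients >18 years or older with ATS definition of severe asthma". Neither the inclusion nor the exclusion list mentions FeNO.

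Nothing says whether a subject at 20-25 ppb is a screen failure, is randomised without a group, or joins the low group. Nothing says how the two screening readings are combined. The analysis text plans a test of the interaction between treatment and FeNO, without saying whether FeNO enters as a category or as a continuous value.

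**The concern.** FeNO group is the effect modifier named in the only aim, and the planned interaction is the test of it. The rule that assigns subjects to groups should therefore be the same at screening, in the eligibility list and in the analysis. Here the screening rule is coarser than the group definition, and the eligibility list does not close the difference.

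A subject in the gap who is randomised has one of two fates, and they are alternatives:

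1. The analysis definition is applied. The subject has no group, has used one of the 50 places, and must be set aside from any categorical FeNO comparison by a decision that the plan does not describe, although it states an intention-to-treat analysis.
2. The screening label is carried forward. The subject is below 25 ppb and is counted as low, contrary to the analysis definition. The low group is then no longer the population in the hypothesis.

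**Working it through.** **Step 1: the rules side by side.**

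| Screening FeNO | Screening line | Aim and analysis text | Barred by eligibility list? |
|---|---|---|---|
| 15 ppb | below 25 | low | no |
| 22 ppb | below 25 | no group | no |
| exactly 20 ppb | below 25 | no group | no |
| exactly 25 ppb | neither | no group | no |
| 30 ppb | above 25 | high | no |

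Two readings such as 19 and 22 ppb cannot be classified without a rule for combining them.

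**Step 2: the plan's own power figure.** Inputs from Clinical trial analysis: N = 50, 10% attrition (45 completers), effect 0.6 SD, alpha 0.025, t-test for a 2x2 cross-over, stated power 95%. I read 0.6 SD as the SD of the within-subject difference and alpha as two-sided. The noncentrality is 0.6 x sqrt(45) = 4.02 on 43 df, and power is 95.2%. The stated figure reproduces. It concerns the overall treatment effect, in which each subject is his or her own control, so it does not depend on FeNO sorting. It does not cover the low-high contrast.

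**Step 3: how many subjects could lie in the gap (assumption only).** The documents give no FeNO distribution. Take it as lognormal with median m and geometric SD g:

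- share of those screened: p = Φ(ln(25/m)/ln g) − Φ(ln(20/m)/ln g)
- share of those below 25 ppb: p / Φ(ln(25/m)/ln g)

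Example, m = 22 and g = 1.8: p = Φ(0.217) − Φ(−0.162) = 0.586 − 0.436 = 0.150, and 0.150/0.586 = 0.26.

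| m (ppb) | g | Share of screened | Share of those <25 | Per 25 subjects <25 |
|---|---|---|---|---|
| 12 | 1.8 | 8.7% | 9.7% | 2.4 |
| 12 | 2.2 | 8.3% | 10.0% | 2.5 |
| 22 | 1.8 | 15.0% | 25.7% | 6.4 |
| 22 | 2.2 | 11.2% | 19.9% | 5.0 |
| 40 | 1.8 | 9.3% | 43.8% | 10.9 |
| 40 | 2.2 | 8.6% | 31.2% | 7.8 |

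The range is about 8-15% of screened subjects and 10-44% of those below 25 ppb.

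**Step 4: what each fate could do to the contrast (illustration).** Assumptions, none from the documents except the borrowed 0.6 SD and the attrition rate: 22.5 completers per group, two-sided 0.05, SD of the within-subject difference 1, true effect 0.6 SD below 20 ppb and 0 above 25 ppb. The normal approximation gives power = Φ(d/SE − 1.96), with SE = sqrt(1/n_low + 1/n_high).

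- Clean groups: SE = sqrt(2/22.5) = 0.298, d = 0.60, power = Φ(2.01 − 1.96) = 52%.
- Counted as low, with a fraction f of the low group in the gap and responding like the high group: d = 0.6(1 − f). For f = 10/20/30/40%, d = 0.54/0.48/0.42/0.36 and power = 44/36/29/23%.
- Counted as low, with half the low-group effect: power = 48/44/40/36%.
- Counted as low, with the full low-group effect: d stays 0.60, and nothing is lost.
- Left without a group, f = 20%: n_low = 18, SE = sqrt(1/18 + 1/22.5) = 0.316, power = Φ(1.90 − 1.96) = 47%. For f = 40%: n_low = 13.5, SE = 0.344, power = Φ(1.74 − 1.96) = 41%.

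**The case against.** The screening entry is one bullet in an outline that calls itself brief. The aim, the design paragraph and the analysis text all give <20 and >25 ppb, and the 25-and-25 recruitment target is repeated in the study design. Recruitment is mainly from the investigator's own clinic, and the investigators take the breath samples. Reading the bullet as shorthand is plausible, and under that reading gap subjects may never have been enrolled. This stands as a limit on what can be claimed: the documents show that the plan permits such enrolment, not that it happened. It does not remove the point, because even as shorthand the bullet leaves the handling of 20-25 ppb unstated, and the eligibility list does not supply it.

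A reader might infer that subjects at 20-25 ppb are enrolled as low and dilute the contrast. The documents do not support that as the consequence. The analysis text fixes low as below 20 ppb, so counting a 22 ppb subject as low would depart from it. Dilution also needs these subjects to respond less than those below 20 ppb, which nothing in the documents supports or denies.

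A reader might also infer that gap subjects necessarily drop out of the interaction test. That is not established either. If FeNO enters as a continuous value they contribute, and the plan does not say which form is used, although the two strata make a categorical reading likely.

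Finally, the analysis section is written in the past tense, so a change to screening may come too late. That stands, and it is why the fix has a reporting part.

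**Conclusion.** The inconsistency is in the text and is not resolved elsewhere: the screening line sorts at 25 ppb, the groups are <20 and >25 ppb, and no eligibility criterion bars the gap. It touches the contrast that the aim is about, so it should be corrected, at moderate priority.

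The number affected cannot be derived from the documents. The 8-15% and 10-44% ranges rest wholly on the assumed lognormal medians and spreads and are not bounds. The power losses in the illustration depend in addition on an assumed difference in response by FeNO. What can be said firmly is that a gap subject, if randomised, either has no group or is misclassified against the analysis definition. The overall within-subject treatment effect and its 95% power are not affected.

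**What to change.** 1. Make the Screening Visit line and the list in Subject Selection, item 5, match the group definitions: below 20 ppb is low, above 25 ppb is high, and 20-25 ppb inclusive is not randomised.
2. State in advance one rule for combining the two screening readings, for example their mean.
3. If any subjects at 20-25 ppb were randomised, report how many. Keep them in the intention-to-treat overall treatment effect, and do not count them as low in the categorical FeNO comparison.
4. State whether FeNO enters the interaction as a category or as a continuous value. A supportive model with continuous baseline FeNO can include the gap subjects.

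The cost is a few lines of text and a small share of screened subjects not randomised (8-15% under the assumptions above), which the <20/>25 design already implies. If enrolment is complete, only the reporting and analysis items apply, and they cost next to nothing.
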